12.1.3 Patient Accrual and Participating Centers

There will be approximately 10 sites collaborating to accrue patients to this study. It is anticipated that accrual will take approximately 2 years.

This trial will be posted at ClinicalTrials.gov website.

12.2 Multi-institutional Guidelines

The trial coordinating center (Operations Center) will be SARC. Patients will be registered electronically via the study website, and adverse events (as defined in Section

7) will be reported to the SARC.

IRB Approvals:

The protocol must be approved at each participating site prior to enrolling patients. Documentation of individual institutional IRB approval, for the current protocol must be provided to SARC prior to enrolling patients in the trial. In addition, documentation of approval of all protocol amendments and of yearly continuing review must be provided to the SARC Research Project Manager to allow patient entry. The mailing address is:

SARC

[name] [contact] [contact] Email: [contact]

Patient Registration:

Patient Registration will be centrally managed by SARC electronically via the study website (see Section 4.2).

Data Collection and Toxicity Reporting:

Registration reports will be generated by SARC RPM to monitor patient accruals and completeness of registration data. Routine data quality reports will be generated to assess missing data and inconsistencies by the Research Project Manager. Any potential problems will be brought to the attention of the site Principal Investigator for discussion and action.

Access to the password protected study website will be limited to individuals involved in the clinical trial: SARC, overall Study PI, participating site PIs, research nurses, and data managers responsible for this trial.

A phone conference will be held between the Study Principal Investigator, the Operations Center, site investigators, and participating sites staff biweekly to address issues, accrual, observed toxicities, and compliance with submission of required studies.

Adverse Events reporting will be performed as outlined in Section 7.

12.3 Data and Participating Site Monitoring

Data from participating sites should be available when the protocol is monitored. The site Principal Investigator is responsible for having all records and data for all patients enrolled at his/her site available at that site for monitoring. Queries as appropriate will be submitted to sites to clarify data. Submission of biologic specimens will be tracked on the study website.

12.4 Handling of Patient Data

All patient data will be captured and maintained in a study specific database with password protected access. Data is entered using an assigned patient identification

number.

The data provided to those reviewing the results, for example the study statistician will include the patient identification numbers, but will not include patient identifiable data.

The research samples obtained in this study will only be sent using the patient identification number which can only be linked to the patient at a given institution by the treating physician.

All documentation that contains personal health information that may include patient identifiable information will be maintained at the site to preserve patient confidentiality.

13. STATISTICAL CONSIDERATIONS

13.1 Study Design/Endpoints

A patient will be classified as a treatment success if he/she achieves a response of PR or better. On each arm of the study, we will test the hypothesis that pembrolizumab has clinical activity in patients with advanced sarcoma. An objective response rate of 25% will be considered clinically meaningful and a response rate less than 10% will be considered lack of efficacy. In a single stage design, we will accrue 40 patients in each arm. The treatment will be considered a success if 8 or more of 40 enrolled patients have a PR or better by RECIST 1.1. This design has a one-sided type I error of 4.2% and a power of 82% to detect a difference between 10 and 25%.

In the study expansion, the response rates for undifferentiated pleomorphic sarcoma cohort and the poorly differentiated/dedifferentiated liposarcoma cohort will be analyzed separately. In each subtype cohort, we will analyze a total of 40 evaluable patients (10 from part 1 of the study and 30 from the expansion cohort). An objective response rate of 25% will be considered clinically meaningful and a response rate less than 10% will be considered lack of efficacy. The treatment will be considered a success if 8 or more of 40 enrolled patients have a PR or better by RECIST 1.1. This design has a one-sided type I error of 4.2% and a power of 82% to detect a difference between 10 and 25%.

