In the initial enrollment and in the first 20 patients of the expansion cohorts (UPS and LPS), preand post-treatment biopsies at week 0 and week 8 are mandatory. Biopsies at cycle 12 (week 34) and at progression are optional. PD-L1 expression, T cell infiltration, as well as suppressor subpopulations will be compared between pre and post-treatment biopsies.

Brief Statistical Design

In the initial enrollment of the study we tested the hypothesis that pembrolizumab has clinical activity in patients with advanced sarcoma. A patient will be classified as a treatment success if he/she achieves a Partial Response (PR) or better by RECIST 1.1. For each arm, an ORR of 25% will be considered clinically meaningful and a response rate less than 10% will be considered ineffective. In this study with a single stage design, we will accrue 40 patients in each arm. The treatment will be considered a success if 8 or more of 40 enrolled patients have a PR or better by RECIST 1.1. This design has a one-sided type I error of 4.2% and a power of 82% to detect a difference between 10 and 25% response rates. This design will also have 87% power to detect an improvement in the 4-months PFS rate from 20% to 40% with a one-sided type I error of 4%.

In the original 86 patient group, 80 patients were evaluable for objective response rate by

RECIST 1.1. Among 40 evaluable patients in the STS cohort, there were 7 partial responses with an ORR of 18%. Four partial responses were seen among 10 patients with undifferentiated pleomorphic sarcoma for an ORR of 40%. Two additional PRs were observed in the dedifferentiated/high grade liposarcoma cohort (2 out of 10) for an ORR of 20%. There was an additional PR seen in the synovial sarcoma cohort. Among 40 evaluable patients in the bone sarcoma cohort, there were 2 partial responses with an ORR of 5%. 1 PR was seen each in the dedifferentiated/high grade chondrosarcoma and osteosarcoma cohorts. Given the observed PRs in the UPS and dedifferentiated/high grade liposarcoma cohorts, we will enroll patients to expansion cohorts to include an additional 30 patients each (UPS and LPS) to further explore and confirm the activity of pembrolizumab.

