In the study expansion, the response rates for undifferentiated pleomorphic sarcoma cohort and the poorly differentiated/dedifferentiated liposarcoma cohort will be analyzed separately. In each subtype cohort, we will analyze a total of 40 patients (10 from part 1 of the study and 30 from the expansion cohort). An objective response rate of 25% will be considered clinically meaningful and a response rate less than 10% will be considered lack of efficacy. The treatment will be considered a success if 8 or more of 40 enrolled patients have a PR or better by RECIST 1.1. This design has a one-sided type I error of 4.2% and a power of 82% to detect a difference between 10 and 25%.

At least 20 patients in each of the undifferentiated pleomorphic sarcoma and poorly differentiated/dedifferentiated expansion cohorts will have mandated biopsies for correlative analysis. The remaining 10 patients in each of the cohorts will not be required to obtain baseline and 8-week tumor biopsies, although archival tissue will be required for PD-L1 testing.

Table of Contents

| SARC Pro | otocol #: 0281 |
|---|---------------------------------------|
| Roles and | Responsibilities of Study Personnel:5 |
| STUDY S | СНЕМА |
| STUDY S | YNOPSIS7 |
| Secondary | 7 Objectives |
| Explorato | ry Objectives7 |
| Trial Desi | gn7 |
| Maximum | Total Number of Patients7 |
| Target Po | pulation7 |
| Efficacy E | valuations |
| Safety Eva | aluations/ Concerns |
| Correlativ | re Studies |
| Brief Stati | stical Design |
| 1. | OBJECTIVES16 |
| 1.1 | Primary Objective16 |
| 1.2. | Secondary Objectives |
| 1.3. | Exploratory Objectives16 |
| 2. | BACKGROUND16 |
| 2.1 | Study Disease16 |
| 2.2 | Study Agent - Pembrolizumab18 |
| Confidential P SARC028 v 5. 180CT2019 | |

Copyright©SARC (Sarcoma Alliance for Research through Collaboration)

| 2.3 | Background | 18 |
|-------------------|---|----|
| 2.4 | Clinical Rationale | 19 |
| 2.5 | General Investigational Approach | 20 |
| 2.6 | Chemical Properties | 20 |
| 2.7 | Structure | 21 |
| 2.8 | Physico-Chemical Properties | 21 |
| 2.9 | Pharmaceutical Formulation | 21 |
| 2.10 | Nonclinical Pharmacology | 21 |
| 2.11 | Affinity and Ligand Blockade of Pembrolizumab | 22 |
| 2.12 Syngeneic | In Vivo Efficacy of Analog Anti-Mouse PD-1 Antibody (as a Monotherapy) in Tumor Models | 22 |
| 2.13 | Non-Clinical Toxicology Summary of Results | 23 |
| 2.14 | Clinical Summary of Results | 23 |

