2.16 Rationale for the Trial and Selected Patient Population

This study is therefore a Phase II clinical trial to determine the preliminary clinical

efficacy of the anti-PD1 antibody pembrolizumab in patients with advanced sarcomas. Given the heterogeneity of advanced sarcomas, the study will have two separate arms that each encompasses sarcoma subtypes with similar anatomic primary sites and patterns of progression.

In the original 86 patient group, 80 patients were evaluable for objective response rate by RECIST 1.1. Among 40 evaluable patients in the STS cohort, there were 7 partial responses with an ORR of 18%. Four partial responses were seen among 10 patients with undifferentiated pleomorphic sarcoma for an ORR of 40%. Two additional PRs were observed in the dedifferentiated/high grade liposarcoma cohort (2 out of 10) for an ORR of 20%. There was an additional PR seen in the synovial sarcoma cohort. Among 40 evaluable patients in the bone sarcoma cohort, there were 2 partial responses with an ORR of 5%. 1 PR was seen each in the dedifferentiated/high grade chondrosarcoma and osteosarcoma cohorts.

Given the observed PRs in the UPS and dedifferentiated/high grade liposarcoma cohorts, we will enroll patients to expansion of both cohorts to include an additional 30 patients each (UPS and LPS) to further explore and confirm the activity of pembrolizumab.

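### The 4.2% and 82% given for the UPS and LPS expansion cohorts take no account of choosing those subtypes on part-1 responses that also count toward 8 of 40, and no estimate in new patients alone is planned

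*Combined protocol and SAP*

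**What the plan says.** Section 13.1 describes part 1 as one single-stage test per arm: "In a single stage design, we will accrue 40 patients in each arm". It takes 10% as inactive and 25% as meaningful, declares success at 8 or more responses in 40, and states: "This design has a one-sided type I error of 4.2% and a power of 82% to detect a difference between 10 and 25" (per cent).

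The next paragraph moves to UPS and LPS, each analysed separately. It says "we will analyze a total of 40 evaluable patients (10 from part 1 of the study and 30 from the expansion cohort"), and then gives the same rule and the same error and power sentence. The synopsis (Brief Statistical Design) does likewise: "we will analyze a total of 40 patients (10 from part 1 of the study and 30 from the expansion cohort").

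The part-1 results were known when this was written. Section 2.16 reports "Four partial responses were seen among 10 patients with undifferentiated pleomorphic sarcoma for an ORR of 40" per cent, and "Two additional PRs were observed in the dedifferentiated/high grade liposarcoma cohort (2 out of 10) for an ORR of 20" per cent. The synopsis gives them as the reason for expanding: "Given the observed PRs in the UPS and dedifferentiated/high grade liposarcoma cohorts, we will enroll patients to expansion cohorts". It also records one responder in a subtype that was not expanded: "There was an additional PR seen in the synovial sarcoma cohort".

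The synopsis and section 2.16 say that the expansion is both to explore activity further and to confirm it. The closing sentence of section 13.3 calls analyses by individual histologic subtype exploratory only. Nowhere are 4.2% and 82% described as figures that ignore the part-1 selection, and no estimate in the 30 new patients alone is planned.

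**The concern.** A type I error and power computed for 40 fresh patients describe the part-1 arms well. They describe the expansion cohorts less well, because a quarter of each cohort had already been observed, had prompted the choice of subtype, and stays in the analysis.

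Two things follow. The pooled 40-patient response rate tends to overstate the true rate, because subtypes with lucky part-1 results are the ones carried forward. And a reader who takes 4.2% as the strength of the expansion evidence may overrate a UPS success, which can be reached with 13.3% responding among new patients. That is close to the plan's own 10% inactivity line and well below the 25% it calls meaningful.

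**Working it through.** **Inputs.** Null rate 10%, target rate 25%, success at 8 or more of 40, composition 10 + 30 (section 13.1). Part-1 responses: UPS 4/10, LPS 2/10 (synopsis and section 2.16). All probabilities are exact binomial; X(n, p) is the number of responders among n patients at true rate p.

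**1. The plan's figures.** P(X(40, 0.10) ≥ 8) = 0.0419 and P(X(40, 0.25) ≥ 8) = 0.8180. The stated 4.2% and 82% reproduce.

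**2. What remained to be shown.** UPS: 8 − 4 = 4 responses in 30 (13.3%). LPS: 8 − 2 = 6 in 30 (20.0%).

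**3. Probability of success given part 1**, P(X(m, p) ≥ k), for m evaluable new patients with the threshold of 8 held fixed. Part 1 had 80 evaluable of 86 patients; the same fraction of 30 is 30 × 80/86 = 27.9, so m = 28 is shown as well.

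| Cohort | k | m | true 10% | true 25% |
|---|---|---|---|---|
| UPS | 4 | 30 | 35.3% | 96.3% |
| UPS | 4 | 28 | 30.5% | 94.5% |
| LPS | 6 | 30 | 7.3% | 79.7% |
| LPS | 6 | 28 | 5.5% | 73.6% |

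These are conditional probabilities of success, not type I error or power. Context for UPS: P(X(10, 0.10) ≥ 4) = 1.3%, so the part-1 result is itself evidence against a true rate of 10%.

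**4. Averaging over selection.** The documents give no selection rule, so a cut-off c is assumed: expand if part 1 has at least c of 10 responses (event S). At a true 10%:

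| c | P(S) | P(S and total ≥ 8) | P(total ≥ 8 given S) | expected pooled ORR given S |
|---|---|---|---|---|
| 1 | 65.1% | 3.9% | 6.0% | 11.3% |
| 2 | 26.4% | 2.9% | 11.1% | 13.3% |
| 3 | 7.0% | 1.5% | 21.4% | 15.5% |
| 4 | 1.3% | 0.5% | 38.5% | 17.9% |

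The last column is (E[part-1 responses given S] + 30 × 0.10)/40. For c = 2, E = (1 − 0.3874)/0.2639 = 2.32, where 0.3874 is P(exactly 1 of 10); hence (2.32 + 3)/40 = 13.3%.

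A cut-off of 2 is compatible with LPS being expanded on 2/10 and synovial sarcoma not being expanded on one response. This supposes one cut-off for all subtypes and 10 synovial patients, and the documents state neither. At c = 2 and a true 25%: P(S) = 75.6%, selected and successful 66.8%, successful if selected 88.4%, expected pooled ORR 26.4%.

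**5. Precision at the minimum success** (exact 95% intervals). Pooled 8/40: 9.1% to 35.6%. New patients only: UPS 4/30, 3.8% to 30.7%; LPS 6/30, 7.7% to 38.6%.

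**The case against.** The strongest reply is that no stated figure is wrong. Type I error and power belong to a rule before data, and this rule has 4.2% and 82%. For a subtype named in advance, being selected and then reaching 8/40 is a subset of reaching 8/40, so 4.2% is an upper bound on that joint chance at a true 10%, whatever the selection rule. All of this stands. A reader might infer that the true type I error for UPS is 35.3%; the documents do not support that, because 35.3% conditions on a part-1 result that itself has probability 1.3% at a true 10%.

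The inputs are also disclosed. The synopsis prints 4/10, 2/10 and the reason for expanding just before the rule, so anyone can subtract the part-1 counts from a pooled result. It would therefore be too strong to say that the information is withheld. What is absent is a planned estimate in new patients and any statement that the quoted figures ignore selection.

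Third, section 13.3 calls subtype analyses exploratory only. That softens the consequence. But the sentence follows the biomarker text, so its reach is arguable. It does not label the figures in 13.1, and it conflicts with the stated aim of confirming activity.

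Finally, the effect on LPS is slight: 7.3% against 4.2%, and 79.7% against 82%. That is right, and the point rests on UPS.

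**Conclusion.** The point holds as one of labelling and estimation, not as an error in sample size or decision rule. The stated 4.2% and 82% are correct pre-data figures that do not account for choosing UPS and LPS on responses that also count toward success. The pooled response rate is biased upward: its expected value is 13.3% at a true 10% under an assumed 2/10 cut-off, and 11.3% to 17.9% over cut-offs of 1 to 4. UPS can succeed with 4/30 new responses; for LPS the effect is small.

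The counts of new responses needed follow directly from the documents. The bias figures rest on the assumed cut-off. A reader might infer that a formal 2/10 rule was applied, but none is stated. The conditional probabilities also rest on the number of evaluable new patients. Severity: minor to moderate.

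**What to change.** Keep the 8/40 rule and the part-1 patients in the pooled analysis. Then:

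- For each cohort, report the response rate with exact 95% interval in the new patients alone, beside the pooled result and with no separate success threshold. Describe the pooled rate as including the patients that led to selection.
- In section 13.1 and the synopsis, label 4.2% and 82% as pre-data figures for 40 patients with unknown outcomes that do not account for selecting the subtypes on part-1 responses. State that success needs at least 4 (UPS) and 6 (LPS) responses among new patients.
- If the conditional success probabilities are printed, state that they are not type I error or power, give the number of evaluable new patients assumed, and add that 4 or more of 10 has probability 1.3% at a true 10%.
- Reconcile the confirmatory aim in the synopsis and section 2.16 with the exploratory status in section 13.3.

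The cost is a few sentences and one table row per cohort, with no extra patients. The downsides are a less favourable reading for UPS and wider intervals: 30.9 percentage points for 6/30 against 26.6 for 8/40.

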2.17 Study Design

This is an open-label, Phase II study of pembrolizumab for patients ≥ 18 years of age with locally advanced, unresectable, recurrent, and/or metastatic soft tissue sarcomas, or ≥ 12 years of age for bone sarcomas. Patients will be assigned to one of 2 arms based on the sarcoma histologic subtypes: high grade aggressive soft tissue sarcomas (specifically leiomyosarcoma, poorly differentiated/de-differentiated liposarcoma, high grade pleomorphic undifferentiated sarcoma/MFH, MPNST and synovial sarcoma), and bone sarcomas (Ewing Sarcoma, osteosarcoma, and chondrosarcoma [de-differentiated or mesenchymal]). The patient population must meet all eligibility criteria specified in Section 3. A total of up to 80 patients will be included in the study. Patients will undergo screening evaluations to determine eligibility within 30 days of the first dose. Each 21 day dosing period will constitute a cycle.

Pembrolizumab is a potent humanized IgG4 anti-PD-1 mAb with high specificity of binding to the PD-1 receptor, thus perpetuates inhibition of PD-L1 and PD-L2 interaction. Based on preclinical *in vitro* data, pembrolizumab has higher affinity and receptor-blocking activity compared to other anti-PD-1 products in development. Pembrolizumab has an acceptable preclinical safety profile and is being advanced for clinical development as an IV immunotherapy for advanced malignancies. Pembrolizumab has been evaluated at 2 and 10 mg/kg every 3 weeks but a flat dose of 200 mg IV every 3 weeks will be utilized for further development.

Patients will be assessed for response (RECIST 1.1) by CT or MRI beginning 8 weeks (\pm 1 week) after treatment initiation and then every 12 weeks (\pm 1 week) until progression or treatment discontinuation, whichever occurs first. Treated patients will

be allowed to continue study therapy after initial RECIST 1.1 defined progression if they are assessed by treating physician to be deriving clinical benefit and tolerating study drug. Treating physician may consult with overall study PI as needed for help with assessing patient. Such patients should discontinue study therapy upon further evidence of progression.

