11.1.1 Definitions

Evaluable for toxicity. All patients will be evaluable for toxicity from the time of their first treatment with pembrolizumab.

Evaluable for objective response. Only those patients who have measurable disease present at baseline, have received at least one cycle of therapy, and have had their disease re-evaluated will be considered evaluable for response. These patients will have their response classified according to the definitions stated below. (Note: Patients who exhibit objective disease progression prior to the end of cycle 1 will also be considered evaluable.)

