11.1.4.3 Evaluation of Tumor Response

11.1.4.4 Best Overall Response when confirmation of CR and PR required

The best overall response is the best response recorded from the start of the study treatment until disease progression/recurrence (taking as reference for progressive disease the smallest measurements recorded since the treatment started). The patient's best overall response assignment will depend on the achievement of both measurement and confirmation criteria.

| Overall response First time point | Overall Response Subsequent time point | Best Overall Response | |
|---|---|---|--|
| CR | CR | CR | |
| CR | PR | SD, PD or PR ^a | |
| CR | SD | SD provided minimum criteria for SD duration met, otherwise PD | |
| CR | PD | SD provided minimum criteria for SD duration met, otherwise PD | |
| CR | NE | SD provided minimum criteria for SD duration met, otherwise NE | |
| PR | CR | PR | |
| PR | PR | PR | |
| PR | SD | SD | |
| PR | PD | SD provided minimum criteria for SD duration met, otherwise PD | |
| PR | NE | SD provided minimum criteria for SD duration met, otherwise NE | |
| NE | NE | NE | |

CR = Complete Response, PR = Partial Response, SD = Stable Disease, PD = Progressive Disease, and NE = Inevaluable

^a If a CR is truly met at first time point, then any disease seen at a subsequent time point, even disease meeting PR criteria relative to baseline, makes the disease PD at that point (since disease must have reappeared after CR). Best response would depend on whether minimum duration for SD was met. However, sometimes 'CR' may be claimed when subsequent scans suggest small lesions were likely still present and in fact the patient had PR, not CR at the first time point. Under these circumstances, the original CR should be changed to PR and the best response is PR.

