13.2 Sample Size/Accrual Rate

Initial enrollment was 86 patients: with soft tissue sarcomas and with bone sarcomas

In the expansion study, there will be an additional 60 patients with soft tissue sarcoma enrolled: 30 patients with undifferentiated pleomorphic sarcoma and 30 patients with poorly differentiated/dedifferentiated liposarcoma.

At least 20 patients in each of the undifferentiated pleomorphic sarcoma and poorly differentiated/dedifferentiated cohorts will have mandated biopsies for correlative analysis. The remaining 10 patients in each of the cohorts will not be required to obtain

baseline and 8-week tumor biopsies, although archival tissue will be required for PD-L1 testing.

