13.4 Reporting and Exclusions

- **13.4.1 Evaluation of toxicity:** Safety evaluations will be done according to CTCAE v 4.0 with special emphasis on immune-related adverse events (ir-AEs).
- **13.4.2 Evaluation of response**: Tumor measurements by CT/MRI imaging will be performed initially at 8 weeks and then every 12 weeks. (RECIST 1.1) will be the primary outcome measure and immune-related Response Criteria (ir-RC) will be a secondary outcome.

Confidential Protocol SARC028 v 3.0:01FEB2018 Copyright©SARC (Sarcoma Alliance for Research through Collaboration)

83

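### Section 13.1 gives two denominators for the primary response rate in the expansion cohorts (40 evaluable, 40 enrolled) and does not say how treated but never re-evaluated patients enter the success rule

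*Combined protocol and SAP*

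**What the plan says.** Section 13.1 describes the expansion analysis of each subtype cohort (UPS and LPS) twice in one paragraph. The analysis set is given as "we will analyze a total of 40 evaluable patients (10 from part 1 of the study and 30 from the expansion cohort"). The decision rule then reads "The treatment will be considered a success if 8 or more of 40 enrolled patients have a PR or better by RECIST 1.1". The synopsis (Brief Statistical Design) repeats the rule but leaves out the word evaluable: "we will analyze a total of 40 patients (10 from part 1 of the study and 30 from the expansion cohort").

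Section 13.2 sets the expansion enrolment at "30 patients with undifferentiated pleomorphic sarcoma and 30 patients with poorly differentiated/dedifferentiated liposarcoma". It makes no allowance for non-evaluable patients and has no replacement rule.

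Section 11.1.1 defines evaluability. Only patients with measurable baseline disease who "have received at least one cycle of therapy, and have had their disease re-evaluated will be considered evaluable for response" qualify. A note adds patients with objective progression before the end of cycle 1.

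The first scan is due at week 8. Scheduled imaging then runs "until progression or treatment discontinuation, whichever occurs first" (section 2.17). Section 10.3 asks for an off-treatment disease evaluation if none was done within 30 days of the final visit.

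Section 13.4 is headed "13.4 Reporting and Exclusions" but contains no exclusion rule. Section 2.16 reports part 1 response rates on 80 evaluable patients out of 86, 40 in each arm.

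**The concern.** Enrolled and evaluable were different groups in part 1, where 6 of 86 patients were not evaluable. A treated patient who dies, withdraws, is lost or deteriorates before any re-evaluation is outside the evaluable set but has not responded. Leaving such patients out removes only failures, so the response rate can only rise.

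The endpoint is primary and is judged by a fixed count of 8. The choice of denominator therefore affects the reported rate. If the number counted is not 40, or if failures are replaced, it also affects whether 8 still gives the stated error rate. The plan leaves three treatments of these patients open: keep them in the 40 as non-responders, replace them, or drop them and keep the cutoff.

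**Working it through.** **Inputs.** Cutoff 8, n = 40, null rate 10%, target rate 25%, stated one-sided type I error 4.2% and power 82% (section 13.1). Expansion enrolment of 30 per cohort (section 13.2). Part 1 evaluability 80/86 = 93.0% (section 2.16); that it recurs in the expansion is an assumption.

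**Reproducing the plan.** With X binomial:
- P(X ≥ 8 | n = 40, p = 0.10) = 0.0419
- P(X ≥ 8 | n = 40, p = 0.25) = 0.8180

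Both match the stated 4.2% and 82%. Like the plan's own figures, all error rates here ignore the part 1 responses already seen.

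**Reading 1: 40 counted, unassessed patients as non-responders.** Nothing changes: 4.2% and 82%, provided 10% and 25% describe all patients counted.

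**Reading 2: 40 treated, unassessed failures dropped, count of 8 kept.** The number of responders is the same, so the decision, error and power are the same. Only the reported rate moves. At the cutoff:
- none dropped: 8/40 = 20.0%
- 2 dropped: 8/38 = 21.1%
- 3 dropped: 8/37 = 21.6%

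**Reading 3: failures replaced until 40 are evaluable, with 10% as the rate among all treated patients.** If m treated non-responders are excluded, 40 + m were treated and the null rate among the evaluable is 0.10 × (40 + m)/40.

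| m | Null rate among evaluable | P(X ≥ 8, n = 40) |
|---|---|---|
| 1 | 0.1025 | 4.7% |
| 2 | 0.1050 | 5.3% |
| 3 | 0.1075 | 6.0% |

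At 80/86 evaluability, 30 evaluable expansion patients need 30 × 86/80 = 32.25 enrolled, so m is about 2 and type I error about 5.3%.

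**For comparison: no replacement, exclusions unrelated to outcome.** The rule becomes 8 of 38 or 39. Type I error is 3.2% or 3.7%, and power is 76.9% or 79.4%. Here the loss is in power.

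**Cutoff when n is not 40.** The smallest cutoff with exact one-sided type I error at or below 5% is 8 for n = 35 to 41 and 9 for n = 42 to 48.

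| n | Cutoff | Type I error | Power |
|---|---|---|---|
| 38 | 8 | 3.2% | 77% |
| 39 | 8 | 3.7% | 79% |
| 41 | 8 | 4.8% | 84% |
| 42 | 9 | 2.1% | 76% |
| 43 | 9 | 2.4% | 78% |
| 44 | 9 | 2.8% | 81% |

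Keeping 8 at n = 42 would give 5.4%.

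**If the 25% target describes evaluable patients only.** The all-treated rate is 0.25 × 80/86 = 0.2326, and P(X ≥ 8 | 40, 0.2326) = 74.4%.

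**The case against.** The strongest reply is that the plan does classify these patients. Section 11.1.1 makes a treated, never re-evaluated patient not evaluable, and part 1 was reported on that basis. This is correct, and a reader who concludes that the documents are silent on such patients goes too far. What stays open is how they count in a success rule written for 40 enrolled.

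Second, part 1 may show the intended practice. Section 2.17 planned up to 80 patients; 86 were enrolled, and exactly 40 per arm were evaluable. That fits enrolment until 40 were evaluable, but the documents do not say so. It is also the practice under which type I error can rise.

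Third, few patients should be affected. Section 10.3 calls for an off-treatment scan, early objective progression counts as evaluable, and section 7.1.1.5 treats progression without imaging support as rare. This stands, and it is why the effect is modest.

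Fourth, a reader might see a further gap in section 11.1.4.4, where best response can be "SD provided minimum criteria for SD duration met, otherwise NE". Those rows concern patients who already had a scan showing CR or PR. They have been re-evaluated, and without PR or better they are not successes under section 13.1. They do not show a denominator gap.

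Fifth, counting all dosed patients could add part 1 patients after their outcomes are known. Under the rule proposed here they enter as non-responders and the cutoff stays or rises, so this cannot make success easier.

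**Conclusion.** The conflict in section 13.1 is real, and it concerns the primary endpoint. Following the evaluable wording biases the response rate upward whenever a treated patient goes unassessed. The size is modest: about 1 percentage point in the reported rate at the cutoff if 2 failures per cohort are dropped (20.0% to 21.1%).

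A reader might infer that the design's type I error exceeds 5%. The documents do not support that as a general statement. The figure of about 5.3% needs three things together: replacement until 40 are evaluable, excluded patients who were dosed and did not respond, and a 10% null defined on all treated patients. It also assumes 2 exclusions per cohort. If the 10% refers to evaluable patients, or the excluded patients were never dosed, 4.2% stands. It also stands if unassessed patients are kept as non-responders, or dropped with the count of 8 unchanged.

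Nor do the documents support restating the part 1 soft tissue rate on a larger denominator. Per-arm enrolment appears to have been lost from the available text, and the reasons for the 6 non-evaluable patients are not given.

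**What to change.** In the synopsis, 13.1 and 13.2, use one primary denominator: all eligible patients who received at least one dose. Count patients with no post-baseline assessment as non-responders. Keep the 11.1.1 evaluable set for a sensitivity analysis only. Replace only patients who are never dosed. Apply the same rule to the part 1 UPS and LPS patients. If a cohort's n is not 40, use the smallest cutoff with exact one-sided type I error at or below 5% (8 for n = 35 to 41, 9 for n = 42 to 48).

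This costs wording and a short cutoff table, with no new data collection. The downsides are a slightly lower reported response rate, power of 76% if n is 42 because the cutoff moves to 9, and about 74% power at 8/40 if the 25% target describes evaluable patients only and 7% are unassessed. The plan should therefore also say which population the 10% and 25% refer to.
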